#### ***INITIAL ASSESSMENT:***

##### **Mini International Neuropsychiatric Interview Version 6.0.0 (MINI or eMINI)**

The MINI is a short structured diagnostic interview developed jointly by psychiatrists and clinicians in the United States and Europe for DSM-IV and International Classification of Diseases 10th Revision psychiatric disorders. With an administration time of approximately 15 minutes, it was designed to meet the need for a short but accurate structured psychiatric interview for multicenter clinical trials and epidemiology studies. It is to be used as a first step in outcome tracking in non-research clinical settings. Validation and reliability studies have been done comparing the MINI to the Structured Clinical Interview for DSM-IV, Patient Edition and the Composite International Diagnostic Interview. The results of these studies showed that the MINI has acceptably high validation and reliability scores, but can be administered in a much shorter period of time (mean 18.7±11.6 minutes, median 15 minutes) than the above referenced instruments.

##### **Adult ADHD Self-Report Scale (ASRS-v1.1) Symptom Checklist**

The ASRS is a tool to help screen for ADHD in adult patients. Insights gained through this screening may suggest the need for a more in-depth clinician interview. The questions in the ASRS are consistent with DSM-IV criteria and address the manifestations of ADHD symptoms in adults. The checklist takes less than 5 minutes to perform.

#### **DESCRIPTION OF CLINICAL OUTCOME MEASURES**

##### ***DEPRESSION:***

##### **Montgomery and Åsberg Depression Scale (MADRS)**

The MADRS is a 10-item rating scale designed to assess the severity of the symptoms in depressive illness that was shown to be sensitive to treatment effects. Items in the scale assess apparent sadness, reported sadness, inner tension, reduced sleep, reduced appetite, concentration difficulties, lassitude, inability to feel, pessimistic thoughts and suicidal thoughts. Symptoms are rated on a 7-point scale from 0 (no symptom) to 6 (severe symptom). Definitions of severity are provided at 2-point intervals. The total score of the 10 items ranges from 0 to 60. An experienced clinician can use the MADRS after a training session. It takes approximately 15 to 20 minutes to administer and rate the MADRS. All efforts will be made to keep the rater consistent.

##### **Hamilton Depression Rating Scale (HDRS)**

The HDRS is a clinician-rated used to rate the patient's depressive state based on feelings of depression, guilt, suicidality, anxiety, agitation, level of insight, patterns of insomnia, loss of interest in work and other activities, weight loss, hypochondriasis, and degree of psychomotor retardation. It also can be used to identify genital and somatic symptoms. This instrument will be administered by an experienced rater meeting the training requirements and qualifications set by the rater training vendor. All efforts will be made to keep the rater consistent.

### **Quick Inventory of Depressive Symptomatology – Self-Report (QIDS-16-SR)**

The QIDS-16-SR is a 16-item self-rated assessment of the severity of depressive symptoms. The QIDS assesses all the criterion symptom domains designated by the American Psychiatry Association Diagnostic and Statistical Manual of Mental Disorders - 4th edition, text revised (DSM-IV-TR) (APA 1994) to diagnose a major depressive episode. These assessments can be used to screen for depression, although they have been used predominantly as measures of symptom severity. The seven day period prior to assessment is the usual time frame for assessing symptom severity.

### **COGNITION AND FUNCTIONALITY:**

#### ***Digit Symbol Substitution Test (DSST)***

The DSST is a cognitive test designed to assess psychomotor speed of performance requiring visual perception, spatial decision-making and motor skills. The DSST consists of 133 digits and requires the subject to substitute each digit with a simple symbol in a 90-second period. The number of correct symbols within the allowed time (eg, 90 sec) is measured. It takes approximately 5 minutes to complete and score the DSST.

#### ***University of San Diego Performance-based Skill Assessment and UPSA-Brief***

The UPSA was designed to evaluate the abilities of individuals to perform everyday tasks that are considered necessary for independent functioning in the community. The UPSA uses role-playing situations to evaluate skills in 5 areas: household chores (eg, preparing a shopping list for a specific cooking task and shopping for items in a mock grocery store); communication (eg, emergency call, dialing a number from memory, calling to reschedule a doctor's appointment); finance (eg, counting change, reading a utility bill, and write and record a check for the bill); transportation (eg, planning the use of a public bus system); planning recreational activities (eg, preparing for an outing to the beach or zoo).

Subscale scores for these scales range from 0 to 20 points, and total scores range from 0 to 100 points; higher scores reflect better performance. Administration of the UPSA requires about 30 minutes to be completed.

#### ***Stroop Test***

The STROOP test [61] is a cognitive test designed to assess the ability to inhibit a prepotent response to reading words while performing a task that requires attention control. The STROOP test comprises 2 sheets with 50 words on each, and each word is the name of a color. On the first sheet, the Congruent STROOP Sheet, the word and ink color match; on the Incongruent STROOP Sheet, the word and ink color do not match. For each sheet, the subject has 4 minutes to name the ink color of each word. When the subject finishes the sheet, or once 4 minutes is up, the clinician notes the time taken and counts the number of correct and incorrect responses. It takes approximately 10 minutes to administer and score the STROOP test.

#### ***Trail Making Test – Part A and Part B (TMT-A AND TMT-B)***

The TMT is a cognitive test designed to assess scanning, visuomotor tracking, executive function, and cognitive flexibility. Both parts of the TMT consist of 25 circles distributed over a sheet of paper. In Part A, the circles are numbered 1–25, and the subject should draw lines to connect the numbers in ascending order. In Part B, the circles include both numbers (1–13) and letters (A–L); as in Part A, the subject draws lines to connect the circles in an ascending pattern, but with the added task of alternating between the numbers and letters (ie, 1-A-2-B-3-C, etc.). The subject should be instructed to connect the circles as quickly as possible, without lifting the pen or pencil from the paper. The subject is timed as he or she connects the "trail." If the subject makes an error, it is pointed out immediately and the subject is

allowed to correct it. Errors affect the subject's score only in that the correction of errors is included in the completion time for the task. It is unnecessary to continue the test if the subject has not completed both parts after 4 minutes have elapsed. It takes approximately 10 minutes to complete the TMT.

### ***Cognitive and Physical Functioning Questionnaire (MGH-CPFQ)***

The Massachusetts General Hospital Cognitive and Physical Functioning Questionnaire is a brief scale used to measure cognitive and executive dysfunction in mood and anxiety disorders. It is a self-report unifactorial scale consisting of 7 items assessing aspects of cognitive and physical functioning, rated on a scale from 1 (greater than normal) to 6 (absent). The reliability and validity of this scale has been evaluated and results have shown it to have strong internal consistency, temporal stability and sensitivity to change with treatment.

### ***Perceived Deficits Questionnaire (PDQ)***

The PDQ is a subject-rated scale designed to assess cognitive function. The PDQ consists of four 5-item subscales: Attention/Concentration, Retrospective memory, Prospective memory and Planning/Organization. Each item is rated on a scale from 0 (never) to 4 (almost always). The total score of the 20 items ranges from 0 to 80 with higher scores reflecting greater subjective cognitive dysfunction. It takes approximately 15 minutes to complete the PDQ.

### ***Working Limitation Questionnaire (WLQ)***

The WLQ has 25 items summarized as 4 scales that represent the percentage of time that a person was limited in particular job demands: time and scheduling demands such as working without stopping or taking breaks and getting going easily at the beginning of the workday (WLQ Time); physical work demands such as sitting, standing or staying in 1 position for longer than 15 min while working and using hand-held equipment (eg, phone) (WLQ Physical); mental-interpersonal work demands such as thinking clearly when working and speaking with people in-person, in meetings or on the phone (WLQ Mental); and output demands, such as working fast enough and doing work without making mistakes (WLQ Output). Scales are scored from 0, limited none of the time, to 100, limited 100 percent of the time. Scores are weighted and aggregated to generate a productivity loss index score. The index is a weighted sum of scale scores that indicates reduction in output per hour compared with the output of a healthy (not limited) employee. This questionnaire will only be administered to subjects who have been employed at least 14 days before baseline.

### ***GLOBAL:***

#### ***Clinical Global Impression Scales (CGI-S and CGI-I)***

The CGI consist of 2 subscales: CGI-S and the CGI-I. The CGI-S assesses the clinician's impression of the subject's current mental illness state. The clinician should use his/her total clinical experience with this subject population and rate the current severity of the subject's mental illness on a 7-point scale. The CGI-I assesses the subject's improvement (or worsening). The clinician is required to assess the subject's condition relative to Baseline on a 7-point scale. In all cases, the assessment should be made independent of whether the rater believes the improvement is drug-related or not.

### ***Assessment of Suicidal Ideation and Behavior***

#### ***Columbia-Suicide Severity Rating Scale ("Lifetime Recent – Clinical" and "Since Last Visit – Clinical")***

The C-SSRS was developed by [name] and researchers at Columbia University as a tool to help systematically assess suicidal ideation and behavior in subjects during participation in a clinical trial. The C-SSRS is comprised of 23 questions divided among four domains addressing suicidal behavior and

suicidal ideation, with sub-questions assessing severity. The scale is administered via clinician interview with the subject.

During the study, the EEG and neuropsychological tests are to be performed preferably at the same time of the day for an individual subject.

## **STATISTICAL ANALYSES**

### **Primary Efficacy Analysis**

The primary endpoint is the change from Baseline in the MADRS and DSST score. The primary endpoint will be analyzed using analysis of covariance (ANCOVA), with treatment and center as fixed factors, and baseline score as covariate. The p-values, least squares (LS) treatment means, difference between the LS treatment means, and 95% CIs for the treatment differences will be displayed.

This is a pilot study that is intended to evaluate the extent of to which BNA technology can provide clinically valuable information, and to provide data that will help design a future confirmatory study. Because this is an exploratory study, no formal sample size calculation was performed; rather, sample size has been based on that which is generally accepted by the medical community for a study of this nature. In order to strengthen the level of confidence of the results, the BNA test is performed twice before the subject is given medication to provide repeatability and two additional times during the course of treatment to allow the identification of any potential trend that may occur as a result of treatment.

The relationship between changes in BNA and BNA total mean change from baseline and endpoint will be analyzed. Changes in BNA from baseline will also be analyzed by groups defined on endpoint status (e.g. response to MADRS, remission, change in DSST).

Statistical analysis should also consider the fact that changes in brain networks may be independent of symptoms or neurocognitive scores; thus, the analysis of BNA changes across treatment duration should be also performed independently. In other words, it is possible that BNA conveys information that is not found in other methods; trying to find correlations may limit the correct interpretation. Therefore, robust trends found in BNA scores should be further researched, regardless of finding correlations to symptoms or neurocognitive tests. For example, it could be that a change in BNA, without a significant change in symptoms, means that if the treatment will be continued for a few more weeks, a delayed improvement will be found; etc.

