### Study Synopsis

This study will include adult outpatients 18-65 years of age with major depressive disorder (MDD) with subjective reporting of cognitive dysfunction treated with flexible-dose vortioxetine (5-20 mg/day) for eight weeks. Following completion of the informed consent process, this study will consist of a screening period (visit 1) of 2-14 days to assess inclusion/exclusion criteria. Subjects who continue to meet inclusion criteria at baseline (visit 2) will begin the assessment and treatment phase of the study.

The first EEG/BNA (BNA) will be performed at the screen visit. Subsequent BNA will be at baseline, 2-weeks after the start of treatment, and at the end of 8 weeks of treatment (or early termination).

The Schedule of Events (Appendix I) shows detailed study procedures that will be performed at each visit. The table below clarifies the schedule of dosing and attendant BNA tests.

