    - i. Subjects meeting antidepressant efficacy criteria (based on response and remission criteria for MADRS, HRSD, QIDS) and improvement in cognition (based DSST).
    - ii. Subjects failing to meet antidepressant efficacy criteria (based on response criteria for MADRS, HRSD, QIDS) but show improvement in cognition (based on DSST).
    - iii. Subjects failing to meet antidepressant efficacy criteria (based on response criteria for MADRS, HRSD, QIDS) and failing to show improvement in cognition (based on DSST).
    - iv.
    - v.
- 5. To explore changes in BNA patterns in MDD with cognitive dysfunction prior to receiving treatment with vortioxetine and:
  - a. Severity of MDD as measured by baseline MADRS total score, QIDS-SR-16 total score, HDRS-28 item total score and CGI-Severity.
  - b. Severity of cognition dysfunction and functionality as measured by baseline DSST, TMT-A/B, TMT-B, Stroop, MGH-CPFQ total score, UPSA, WLQ.
  - c. Prediction of achieving symptomatic remission of MDD as measured by remission status on MADRS total score, HDRS-17 total score and CGI-Improvement (1 or 2)
  - d. Prediction of cognitive improvement measured by DSST score; cutoff 70% improvement from baseline.
- 6. Explore relationship with changes in BNA patterns in remitted vs. non-remitted subjects after 8 weeks of treatment with vortioxetine as measured by MADRS total score, HDRS-17 total score, QIDS total score,, and CGI-Improvement.
- 7. Assess safety and tolerability of 8 weeks open-label, flexible-dose vortioxetine in all subjects for:
  - a. Spontaneously reported adverse events
  - b. Clinical safety laboratory tests (when indicated, vital signs, weight, EKGs and physical exam)

- c. Evaluate relationship between adverse events after 2 and 8 weeks of treatment with changes in BNA patterns for nausea, worsening of baseline suicidal ideation (as measured by MADRS item 10, HDRS-17 item 2 and C-SSRS)

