### **Secondary Efficacy Analyses**

Change from Baseline in TMT A, TMT B, , PDQ, MGH-CPFQ, UPSA, percentage of productivity loss (WLQ), MADRS, CGI-S, and CGI-I will be analyzed at all time points (where rated) using ANCOVA model similar to the one described above for the primary endpoints.

MADRS responders (defined as a >50% decrease from Baseline), MADRS remission (defined as a MADRS total score <10). CGI-S remission (CGT-S2), and CGI-I response (CGI-I2) will be analyzed at all time points by logistic regression, adjusting for baseline score and treatment.

Proportion of cognitive dysfunction improvement that is not due to an improvement in depressive symptoms will be analyzed using a path analysis with change from Baseline in DSST score and change from Baseline in MADRS total score as endogenous variables.

C-SSRS will be summarized at all time points using descriptive techniques.

All statistical tests will be 2-sided and at the 5% level of significance. Ninety-five percent confidence limits will be presented together with the p-values.

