**Antidepressant medication (vortioxetine)**

At the time of informed consent, the subject will be instructed about the risks and benefits of the vortioxetine that will be used throughout the study.

The potential risks of the medication will be based upon the FDA-approved package insert labeling for vortioxetine and will include, but not limited to, spontaneous reported adverse events and potential serious adverse events. Source documents will contain documentation that the subject was informed of risks of treatment and that there was adequate time to read and discuss this information with the clinician during the informed consent process.

The FDA-approved package insert for vortioxetine recommends a starting dose of 10 mg/day, increased to 20 mg/day as tolerated. The maximum dose is 20 mg/day, and the minimum dose is 5 mg/day if a higher dose is not tolerated. This allows for individualized “flexible” dosing for efficacy and tolerability.

In order to standardize this flexible dosing, all subjects will be started at 10 mg/day following visit 2 (baseline). The dose will be increased to a maximum of 20 mg/day after visit 4 (2 weeks of treatment) if tolerated by the subject. Dose decreases may occur at any time until Visit 8 for tolerability issues, to a minimum dose of 5 mg/day, and the dose may be re-increased if the tolerability issue resolves.

No dose adjustments may take place after visit 8 through the end of treatment (Visit 10).

Safety, tolerability, and depressive symptoms/function assessments will occur at baseline and each subsequent visit through the end of the study. While this is an exploratory analysis, the impact of treatment at various points in the study will be analyzed. Baseline assessments will occur prior to the subject receiving medication.

Drug accountability will be recorded at all visits. Subjects failing to meet at least 80% adherence to study medication between study visits will be discontinued from the study.

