#### **Recruitment**

The study population will be recruited from the greater Chicago metropolitan area. Subjects will be recruited from several sources, including referrals, responders to our general depression recruitment (advertisements on craigslist, newspapers, radio, the PMA website, private practice settings and community health centers). Subjects will also be recruited from ongoing clinical trials at Psychiatric Medicine Associates, LLC (PMA). Subjects may also be recruited from other trials only if considered appropriate for an open label treatment study with vortioxetine and do not meet other exclusion criteria. This is a study of depression in adults and therefore children will be excluded.

Subjects will be reimbursed for appropriate travel expenses during participation in the study.

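### The ANCOVA for MADRS and DSST promises a between-treatment difference that a one-arm trial cannot produce; the adjusted mean change should be named as the result

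*Combined protocol and SAP*

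**What the plan says.** The Primary Efficacy Analysis section of the combined protocol and SAP takes change from baseline in MADRS and DSST as the primary endpoint. The model is given as: "The primary endpoint will be analyzed using analysis of covariance (ANCOVA), with treatment and center as fixed factors, and baseline score as covariate". The outputs follow: "The p-values, least squares (LS) treatment means, difference between the LS treatment means, and 95% CIs for the treatment differences will be displayed".

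Secondary Efficacy Analyses applies this to the other continuous measures, "using ANCOVA model similar to the one described above for the primary endpoints", and adjusts the logistic models for response and remission for baseline score and treatment. It also sets a general reporting rule: "Ninety-five percent confidence limits will be presented together with the p-values".

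On the design, the Study Synopsis has subjects "treated with flexible-dose vortioxetine (5-20 mg/day) for eight weeks". Item 7 of the Secondary Outcomes reads "Assess safety and tolerability of 8 weeks open-label, flexible-dose vortioxetine in all subjects for". The section on the antidepressant medication starts everyone on the same dose. Recruitment admits subjects from other trials "only if considered appropriate for an open label treatment study with vortioxetine". The visit summary and Appendix I show one visit track common to all subjects.

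**The concern.** An analysis of covariance yields a treatment difference only if at least two treatments are represented in the data, and here there is one. The paragraph headed as the primary efficacy analysis therefore names, as its main comparative output, a quantity that the design cannot supply.

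Software would drop the redundant term without complaint. The factor tests left in the output would then concern center and baseline slope, and neither is a test of efficacy. The text does not say what null hypothesis a p-value would test once the treatment contrast is gone. The study is meant to inform a later confirmatory trial, so a reader needs to know which MADRS and DSST estimate will be reported. That is better settled before the results are seen.

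**Working it through.** The plan gives no effect size, SD or power for this analysis and states that no formal sample size calculation was done. There is no figure to reproduce, so the check is one of estimability.

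**Inputs**
- Subjects: 40 (Number of Subjects).
- Centers: 2 (Number of Sites).
- Treatments: 1 (sections cited above).
- Model terms: treatment, center, baseline score (Primary Efficacy Analysis).
- Tests: two-sided at 5% (Secondary Efficacy Analyses).

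**Step 1: rank of the planned model.** The columns are intercept, treatment, center and baseline. Every subject has the same treatment value, so the treatment column equals the intercept.
- Rank with treatment: 3 of 4 columns.
- Rank without treatment: 3 of 3 columns.
- Degrees of freedom for treatment = 3 − 3 = 0.

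**Step 2: is the contrast estimable?** Code treatment as two levels, the second empty, with columns intercept, vortioxetine, other, center, baseline. The contrast is c = (0, 1, −1, 0, 0). It is estimable only if projecting it onto the row space of the design matrix returns c. The projection is (0.5, 0.5, 0, 0, 0), which is not c. The difference is not estimable, and adding subjects to the same single arm does not change this.

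**Step 3: could treatment mean something else?**
- *Dose level.* Dosing is flexible and driven by tolerability. No dose groups are defined.
- *Before versus after.* The response is already a change from baseline, so time cannot also be the treatment factor.
- *Controls.* The BNA Analysis section mentions controls and other contrasts when it describes how the algorithm and ROC analysis work. No control cohort is enrolled or treated.
- *Arm and group wording.* BNA Analysis refers to an arm receiving drug, and the Clinical Evaluations part of Safety Analyses refers to treatment groups. Neither defines a second group.
- *Responder groups.* The plan uses groups defined by endpoint status separately, for BNA change.

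**Step 4: what remains.** Without treatment, the model (intercept, center, baseline) has full rank 3 and 40 − 3 = 37 residual degrees of freedom. Evaluated at the mean baseline with centers weighted by enrolment, the adjusted mean change has

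95% half-width = t(0.975, 37) / √40 = 2.026 / 6.325 = 0.320 residual SD.

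The documents give no SD of change, so this cannot be turned into scale points. The evaluation point does need stating. If baseline is left uncentered, the intercept refers to a baseline score of zero, whereas inclusion requires a MADRS total of at least 26.

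**The case against.** The best defence is that this is template wording with little consequence. The same paragraph makes change from baseline the endpoint and lists LS means among the outputs. With one arm there is only one such mean, and the secondary section already attaches 95% limits to p-values. The study is labelled exploratory, and no sample size or decision rule depends on the contrast. Most of this stands, and it is why the harm is moderate. It does not make the listed difference computable, and it does not supply a null hypothesis for a single-arm p-value.

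Two stronger readings are tempting, but the documents do not support them.
- A reader might infer that the trial's primary analysis fails altogether. The Primary Outcome section relates BNA change to MADRS response status and DSST change, and none of that uses the treatment term. The logistic models also remain usable once the redundant term is removed.
- A reader might infer that precision will be appreciably worse than the figure above, through attrition or unequal centers. The plan states no dropout rate and no center split. The consent-only definition of an enrolled subject applies to IRB reporting; for data analysis, a subject must have completed the baseline visit. Stating how centers are weighted is good practice, but its absence is not the defect here.

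**Conclusion.** The point holds and should be fixed. As written, the between-treatment part of the MADRS and DSST analysis cannot be run: treatment has 0 degrees of freedom, so its difference, p-value and 95% interval cannot be produced at any sample size. The same term is redundant in the secondary ANCOVAs and logistic models. This rests only on there being one treated group, which the synopsis, outcomes, dosing, recruitment and schedule sections all support.

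The consequence is limited. No data and no obtainable result are lost, and the single-arm LS mean change survives. The 0.32 residual SD half-width is given for scale only. It assumes that all 40 subjects are evaluable and that centers are weighted by enrolment, and it does not measure the defect.

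**What to change.** - In Primary Efficacy Analysis, delete treatment from the ANCOVA and delete the treatment-difference outputs.
- State the MADRS and DSST result as the mean change from baseline with its 95% confidence interval, adjusted for center and baseline score and evaluated at the mean baseline.
- Describe it as within-subject change without a control.
- If a p-value is kept, state that it tests zero mean change.
- In Secondary Efficacy Analyses, remove treatment from the ANCOVA and logistic models.
- As a conforming edit, remove the reference to treatment groups in the Clinical Evaluations part of Safety Analyses.

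The cost is a wording amendment, which under the IRB Review section needs prior written approval. It needs no new subjects, visits or data.

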### Number of Sites: (U.S. Study)

2: Chicago, IL and Skokie, IL

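### In this one-arm trial the planned ANCOVA yields only a least squares mean change, whose centre weights and interval are undefined and whose model-based 95% limits are too narrow for the population mean change where change depends on baseline

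*Combined protocol and SAP*

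**What the plan says.** The statistical section opens with two change scores: "The primary endpoint is the change from Baseline in the MADRS and DSST score". The model follows: "The primary endpoint will be analyzed using analysis of covariance (ANCOVA), with treatment and center as fixed factors, and baseline score as covariate". The promised output is p-values, LS treatment means, the "difference between the LS treatment means, and 95% CIs for the treatment differences will be displayed".

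Secondary Efficacy Analyses carries the approach to TMT-A, TMT-B, PDQ, MGH-CPFQ, UPSA, WLQ productivity loss, MADRS, CGI-S and CGI-I, "using ANCOVA model similar to the one described above for the primary endpoints". It ends with a general rule: "Ninety-five percent confidence limits will be presented together with the p-values".

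The design has one arm. The safety outcome refers to "Assess safety and tolerability of 8 weeks open-label, flexible-dose vortioxetine in all subjects for", and the dosing text starts all subjects on the same drug after baseline. Forty subjects are planned. The sites are given as "2: Chicago, IL and Skokie, IL", with no split between them.

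The plan does not give LS-mean weights, the baseline value at which the LS mean is taken, an SD, a baseline-endpoint correlation, or an interval defined for single-arm mean change.

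**The concern.** With a one-level treatment factor there is no difference to estimate. That is a separate and more basic defect, and deleting the factor does not settle what follows. What remains is an LS mean change adjusted for centre and baseline, and two of its features matter in a single arm although they largely cancel in a two-arm comparison.

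First, the model-based standard error uses the residual SD around the baseline regression at the observed mean baseline. It treats that mean as known. If the limits are meant to describe mean change in the population sampled, the sampling variation of baseline has been left out.

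Second, an LS mean has to average over the two centres by some rule. Many programs weight factor levels equally unless told otherwise, so a small site could count as much as a large one.

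The protocol wants this pilot to help design a confirmatory study. Mean changes and their uncertainty are direct inputs to that design, so an interval narrower than its stated confidence would mislead.

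**Working it through.** **Inputs from the documents.** One arm; N = 40 (Number of Subjects); two centres (Number of Sites); fixed centre and baseline covariate (Primary Efficacy Analysis); two-sided 5% level and 95% limits (Secondary Efficacy Analyses). The plan gives no sample-size calculation or interval width, so there is no figure of its own to reproduce.

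**Assumed, with ranges.** Centre splits from 20/20 to 35/5; baseline-endpoint correlation r of 0.2 to 0.6 with equal SDs; MADRS-like SDs of 4 then 9 with r = 0.3; DSST-like SDs of 11 then 12 with r = 0.8.

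**Step 1: what the model can estimate.** With treatment at one level, the columns for intercept, treatment, centre and baseline number 4 but have rank 3. No treatment contrast exists; an LS mean change does.

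**Step 2: holding baseline fixed.** Let rho be the correlation of change with baseline. With a 20/20 split, the ratio of the ANCOVA width to the one-sample t width is about sqrt(1 - rho²). The true sampling SD of the estimate is not reduced by that factor, so coverage is about 2Φ(1.96 × ratio) - 1.

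With equal SDs at both visits, rho = -sqrt((1 - r)/2), so the ratio is sqrt((1 + r)/2):

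| r | rho | Width ratio | Approximate coverage | Simulated coverage |
|---|---|---|---|---|
| 0.6 | -0.45 | sqrt(0.8) = 0.89 | 92.0% | 92.4% |
| 0.4 | -0.55 | sqrt(0.7) = 0.84 | 89.9% | 90.0% |
| 0.2 | -0.63 | sqrt(0.6) = 0.77 | 87.1% | 87.3% |

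The simulation used 20,000 trials of 40 subjects per row. The one-sample t interval covered 95% in each row.

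**Step 3: the two primary scales.** In general rho = (r·s0·s1 - s0²)/(s0·SD of change), where s0 and s1 are the SDs at baseline and endpoint.

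- MADRS-like: the covariance of change with baseline is 0.3 × 4 × 9 - 16 = -5.2. The variance of change is 16 + 81 - 21.6 = 75.4 (SD 8.68). So rho = -5.2/(4 × 8.68) = -0.15 and the ratio is 0.989.
- DSST-like: the covariance is 0.8 × 11 × 12 - 121 = -15.4. The variance of change is 121 + 144 - 211.2 = 53.8 (SD 7.33). So rho = -15.4/(11 × 7.33) = -0.19 and the ratio is 0.982.

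The width falls by 1-2%, and simulated coverage is about 94.5% for both.

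**Step 4: centre weights, if equal.** Relative to the average over subjects, the variance is multiplied by N²/(4·n1·n2):

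- 20/20: 1600/1600 = 1.00, so the standard error is unchanged.
- 30/10: 1600/1200 = 1.33, standard error x1.15.
- 35/5: 1600/700 = 2.29, standard error x1.51.

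When change does not depend on baseline and the centres do not differ, simulated coverage is 0.950 at 30/10 and 0.948 at 35/5. This is lost precision, not miscalibration. If the centres differ by an assumed 0.5 SD with |rho| = 0.5, coverage of the subject-weighted mean is 0.85 at 30/10 and 0.84 at 35/5. That loss comes mainly from aiming at a different mean.

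**Step 5: the effects combined.** The width ratio is about sqrt(1 - rho²) × sqrt(N²/(4·n1·n2)). At 30/10 with |rho| = 0.5 it is 0.866 × 1.155 = 1.00, yet simulated coverage is 0.92. Equal width is therefore no guarantee of correct coverage.

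**Step 6: is re-weighting enough?** With observed-margin weights the LS mean at the mean baseline equals the arithmetic mean, because least squares residuals sum to zero. The model-based standard error still holds baseline fixed: at |rho| = 0.5 the width ratio stays at 0.87 and coverage at 0.90 to 0.92.

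**The case against.** A reader might infer that the plan prescribes equal centre weights and so commits itself to intervals of the wrong width. The documents do not support that. Equal weighting is a common software default, and observed margins fit the text just as well. Where equal weights are used, the interval is valid for the equal-weight centre mean. Preferring the average over subjects is a choice of target, and nothing in the documents suggests that the centres differ.

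Nor does the plan expressly promise an interval for mean change. Primary Efficacy Analysis promises intervals for treatment differences, and limits for the LS mean follow only from the general sentence in the secondary section.

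It can also be said that conditioning on the observed baselines is ordinary ANCOVA practice, that the direction of the net effect depends on an unstated split and correlation, and that this is an exploratory pilot with no decision threshold tied to these limits. The entry limits on MADRS and DSST restrict baseline spread, which makes the equal-SD case less apt for those two scales.

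All of this stands, and it narrows the point. It does not remove it. Limits conditional on baseline are sound for a conditional statement, but a reader will take a reported mean change with 95% limits as a statement about the population, and for that reading they under-cover. The plan does not say which is meant.

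**Conclusion.** The point holds in a limited form. The model can return only an LS mean change here, and its weights and interval are undefined. Read as limits for the population mean change, the model-based 95% limits cover about 92% to 87% across the assumed correlations of 0.6 to 0.2, given equal SDs and a 20/20 split. Those inputs are assumptions, and weaker dependence on baseline gives a smaller shortfall.

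It would be wrong to conclude that the MADRS and DSST intervals are materially distorted by fixing baseline: under the assumed values the effect is 1-2% of width. The practical weight falls on secondary scales such as the PDQ and MGH-CPFQ. The centre issue is conditional on equal weights and an unequal split. It is then a loss of precision and, only if the centres differ, a change of target. The correction is worth making because it is nearly free and gives a better-calibrated single-arm estimate.

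**What to change.** In both efficacy analysis sections, name the quantity as mean change from baseline over all subjects with data. Report it with a one-sample t 95% interval for MADRS, DSST and each secondary scale that has a pre-treatment value. Name that value for each scale: in Appendix I the DSST, TMT and UPSA are rated before treatment at screening only.

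Three details are needed:

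- **CGI-I** is already a rating relative to baseline and is first collected at Visit 3. Summarise the observed score, not a change.
- **WLQ** is given only to employed subjects. Use that number, not 40.
- **Centre** means should be shown descriptively.

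If the ANCOVA is kept, specify observed-margin centre weights and an interval that includes baseline sampling variation, for example a bootstrap stratified by centre. Unstratified resampling is unsafe if one site is very small: with a 38/2 split, about 0.95^40 = 13% of resamples would contain nobody from that site.

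The cost is SAP wording, with no new data. Some secondary intervals will be wider than the planned model would have shown.
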